10.1.2 Pharmacokinetic Endpoints

CSF elimination half-life and trough drug levels will be assessed, where appropriate. Urinary excretion parameters such as amount of drug excreted and renal clearance will be determined, as appropriate.

10.1.3 Pharmacodynamic and Clinical Endpoints

Biochemical

- Neuroimaging volumes, including but not limited to:
 - o Structural MRI
 - Caudate volume
 - Whole brain volume
 - Ventricular volume

- Electrophysiological
 - o qEEG
- Clinical

- Cognitive and motor tests:
 - HD Cognitive Battery

10.2 Sample Size Considerations

The sample size is dictated by the number of patients enrolled in the prior MAD study (Study ISIS 443139-CS1). Based on experience with generation 2 ASOs administered by IT injection, this number of patients ($N \approx 46$) is expected to be sufficient to ensure that the safety, tolerability, pharmacokinetics and pharmacodynamics are adequately assessed.

10.3 Populations

Safety Population: All patients who are randomized and receive at least 1 dose of *RO7234292*.

Per Protocol Population: All patients who are randomized and receive all protocol-specified doses of RO7234292.

PK Population: All patients who are randomized to RO7234292 and receive at least 1 dose of RO7234292 and have sufficient sampling to permit pharmacokinetic evaluation.

10.4 Definition of Baseline

For vital signs (BP, HR, respiration rate and temperature), baseline will be defined as the average of the values collected prior to first dose (Screening, Study Day -1 and Study Day 1). For CSF laboratory tests, baseline will be defined as the average of the values collected prior to first dose (Screening and Study Day 1). For all other measures and parameters, baseline will be defined as the last non-missing measure prior to the first dose.

10.5 Interim Analysis

The Sponsor may choose to conduct one or more interim analyses including safety, PK, PD biomarkers and clinical endpoints as relevant. Details of each interim analysis will be described in a dedicated SAP, which will be finalized before the conduct of the interim analysis.

10.6 Planned Methods of Analysis

All CRF data, lab data transfers, and any outcomes derived from the data will be provided in the patient data listings. Patient data listings will be presented for all patients enrolled into the study. Descriptive summary statistics including n, mean, median, standard deviation, standard error, interquartile range (25th percentile, 75th percentile), and range (minimum, maximum) for continuous variables, and counts and percentages for categorical variables will be used to summarize most data. Where appropriate, comparisons between regimens may be conducted and p-values may be reported. Statistical tests will be conducted using 2-sided tests with 5% Type I error rate unless otherwise stated in the Statistical Analysis Plan (SAP).

10.6.1 Demographic and Baseline Characteristics

Demographic and baseline characteristics will be summarized using descriptive statistics by regimen. Patient disposition will be summarized by regimen. All patients enrolled will be included in a summary of patient disposition.

10.6.2 Safety Analysis

The safety analysis will be conducted on the Safety Population.

Treatment duration and amount of RO7234292 received will be summarized by regimen.

All treatment-emergent adverse events (TEAEs) and SAEs will be summarized for each regimen and for all patients using the Medical Dictionary for Regulatory Activities (MedDRA) coding system by system organ class, preferred term, relationship to Study Drug, and severity.

Narratives of "on-study" deaths, serious and significant AEs, including early withdrawals due to AEs, will be provided.

Laboratory tests to ensure patient safety including chemistry panel, hematology panel, CSF safety labs (cell counts, protein, glucose) and urinalysis, will be summarized by study visit for each regimen. These safety variables will also be presented as change and percent change from baseline over time, as appropriate.

Vital sign and ECG measures will be tabulated by regimen. In addition, the number of patients who experience abnormalities in clinical laboratory evaluations will be summarized by regimen.

Columbia – Suicide Severity Rating Scale will be summarized by study visit for each regimen. Physical examination, standard neurological assessment (including fundi), and clinical and neuroimaging results will be summarized, if appropriate, and listed.

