Study Design	This is an open-label extension (OLE) of Study ISIS 443139-CS1. Study ISIS 443139-CS1 was a multiple-ascending dose (MAD) study in 46 patients with early manifest HD aged 25-65 years, inclusive. In the MAD study, patients received 4 doses of ISIS 443139 or placebo. Eligibility for Study $BN40697$ (ISIS 443139-CS2) is based on completion of the 4-dose Treatment Period of the prior MAD study and absence of deterioration in health or intervening activities that would introduce risk to the patient sufficient to preclude participation in the OLE.
	This is a multi-center study with study duration of up to 18 calendar months. Two (2) dosing regimens will be tested – monthly and bimonthly. Randomization between regimens (1:1) will be stratified by Study Center.
	 "Monthly" regimen: administrations of RO7234292 every 28 days for 62 weeks (2-dose Loading Period followed by 14-dose Maintenance Period)
	 "Bimonthly" regimen: 2 administrations of RO7234292 separated by 28 days (2-dose Loading Period) followed by administrations every 56 days for 56 weeks (7-dose Maintenance Period)

Study Design Continued	The $RO7234292$ doses used in these regimens will not exceed 120 mg/dose, the highest dose evaluated in the prior MAD study.
	A final visit will be held approximately 14 weeks after the last dose.
	The extent of screening procedures required for this study varies depending on the amount of time that has elapsed between participation in the MAD study and the start of the OLE (see Appendix A, Schedule of Procedures).
Number of Subjects	Up to 46 (patients who previously participated in ISIS 443139-CS1)
Study Population	Inclusion Criteria
	Signed Written Informed Consent
	Must have given written informed consent (signed and dated) and any authorizations required by local law and be able to comply with all study requirements
	Must be capable of giving informed consent (in the opinion of the Investigator)
	Target Population
	3. Must have completed the Treatment Period of Study ISIS 443139-CS1
	Able and willing to meet all study requirements in the opinion of the Investigator, including:
	Adequately supportive psychosocial circumstances

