Safety and Tolerability	Safety and tolerability evaluations include:
Evaluations	Columbia - Suicide Severity Rating Scale (C-SSRS)
	Physical examination and standard neurological assessment (including fundi)
	Pregnancy testing
	Vital signs (HR, BP, orthostatic changes, weight)ECG
	AEs and concomitant medications
	CSF safety labs (cell counts, protein, glucose)
	Plasma laboratory tests (clinical chemistry, hematology)
	Urinalysis
	Neuroimaging assessments (safety sequences)
	The safety and tolerability of $RO7234292$ will be assessed by determining the incidence, severity and dose-relationships of AEs, ECG changes and changes in laboratory parameters by dose.
Pharmacokinetic Evaluations	CSF samples will be used for evaluation of pharmacokinetic parameters.
	Concentration of $RO7234292$ in CSF will be summarized using descriptive statistics and the $RO7234292$ half-life in CSF will be calculated, if possible.
	Concentration of RO7234292 in urine
	following first dose will be summarized.
Pharmacodynamic and Clinical	Pharmacodynamic and clinical evaluations include:
Evaluations	Mutant Htt protein level in CSF and other plausible fluid biomarkers of Huntington's disease progression
	Structural MRI (ventricular, caudate and whole brain volumes),
	Quantitative electroencephalography
	Assessments of physical functioning, activities of daily living, gait, mobility, cognitive functioning and neuropsychiatric condition

Pharmacodynamic and Clinical Evaluations Continued	Evaluations will include comparisons between Monthly and Bimonthly Cohorts, where appropriate, and correlations between pharmacokinetic and pharmacodynamic parameters.
Statistical Considerations	The sample size is dictated by the number of patients enrolled in the prior MAD study (Study ISIS 443139-CS1). Based on experience with generation 2 ASOs administered by IT injection, this number of patients (N \approx 46) is expected to be sufficient to ensure that the safety, tolerability, pharmacokinetics and pharmacodynamics are adequately assessed.
Sponsor	F. Hoffmann-La Roche Ltd

STUDY DESIGN AND TREATMENT SCHEMA

SCREENING PERIOD

Weeks -4 to -1

- Assess capacity to consent, collect informed consent
- Assess eligibility
- Collect CSF

COHORT ASSIGNMENT

- Patients are allocated to:
 - Monthly Cohort or
 - Bimonthly Cohort

LOADING PERIOD

Weeks 1 to 6

• Each patient receives 2 doses of RO7234292, with doses 28 days apart

MAINTENANCE PERIOD

Weeks 7 to 62

[figure not shown]

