6.1.1 Screening Period (Week -4 to Week -1)

Written informed consent for the study will be obtained prior to the performance of any study-related procedures including screening procedures. During the Screening Period, inclusion/exclusion criteria will be evaluated to determine patient eligibility for the study. A single CSF sample will be collected during the Screening Period. At least 2 weeks must elapse between the screening CSF collection and Study Day 1. Abnormal laboratory screening results may be retested for review by the Study Medical Monitor for eligibility purposes.

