6.1.2 Treatment Period (Week 1 to Week 62)

During the Loading Period, RO7234292 will be administered 2 times, with doses separated by 28 days. During the Maintenance Period, RO7234292 will be administered either every 28 days (Monthly Cohort) or every 56 days (Bimonthly Cohort) according to regimen assignment at randomization.

Eligible patients will report to the Study Center on Study Day -1 (the day prior to first RO7234292 administration) for baseline assessments. Assessments should be completed at approximately the same time of day from visit to visit. At the completion of assessments on Study Day -1, patients will be discharged unless the Investigator feels it is in the patient's best interest for him/her to remain in the Study Center overnight. Patients will return to the Study Center on Study Day 1 to undergo CSF sampling and RO7234292 administration via lumbar puncture, followed by overnight observation in the Study Center, safety assessments on Study Day 2 and then discharge. On Study Day 3, the Study Center will conduct a brief visit with the patients by phone to capture any AEs or changes in concomitant medication usage. (See Appendices A and C.) On Study Day 8, the patients will return to the Study Center for additional assessments.

Subsequent RO7234292 administrations will be conducted in a similar manner, with pre-dose assessments conducted either the day before or the day of RO7234292 administration, in-clinic observation of at least 5 hours after RO7234292 administration (longer or overnight if necessary for safety reasons) and in-clinic assessments or phone assessments on the days following RO7234292 administration.

All patients, regardless of cohort assignment, will appear at the Study Center at least every 4 weeks throughout the Treatment Period for routine monitoring.

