6.2.18 Collection of CSF

Patients will have CSF collected at the Screening Visit, prior to administration of each dose of RO7234292 and at the Post-Treatment Visit. At each collection, 20 mL of CSF fluid is to be collected for analyses. If there are difficulties in collecting 20 mL of CSF fluid, a minimum of 15 mL should be collected. A 24G atraumatic needle (Whitacre or other if approved by Sponsor prior to use) will be used. Depending on institutional guidelines, local anesthesia may be used for the procedure. Sedation may not be used. Spinal ultrasound may be used for the LP procedure, if deemed necessary, but is not required.

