8.7 Adjustment of Dose and/or Treatment Schedule

For a given patient, no adjustment of dose is planned. If a situation prevents the dosing procedure (i.e., lumbar puncture) from being performed safely but discontinuation of RO7234292 is not warranted, an adjustment in the dose schedule may be permitted at the discretion of the Investigator, in consultation with the Sponsor Medical Monitor. Examples of situations where the dosing schedule may be altered include the following:

- If a clinically significant abnormality is observed in the laboratory tests conducted prior to lumbar puncture (protocol Section 6.2.19.1) that increases lumbar puncture-related risk to the patient, further lumbar punctures must be delayed to allow for investigation into the finding. Prior to resuming treatment, the Investigator and Medical Monitor must agree to resume dosing.
- If patient is experiencing a concurrent illness that increases lumbar puncture-related risk to the patient, such as a skin infection near the area for injection, further lumbar punctures must be delayed until Investigator and Medical Monitor agree to resume dosing.

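### The *Possible* category in Section 9.4.3.1 is stricter than the suspected-adverse-reaction standard in Section 9.3.2, so some well-timed events have no causality category

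*Combined protocol and SAP*

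**What the plan says.** Section 9.3.2 defines a suspected adverse reaction as an AE that the drug may, as a reasonable possibility, have caused. It adds that this is a lower degree of certainty than an adverse reaction.

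Section 9.4.3.1 asks the investigator to choose one of four ratings:

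- *Related* needs clear evidence.
- *Possible* needs plausible timing and no explanation from the patient's condition, other therapy or other causes.
- *Unlikely/Remote* needs an alternative that is more likely, or timing that argues against the drug.
- *Not Related* needs a ready alternative explanation and the investigator's belief that there is no relationship.

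For reporting, *Unlikely/Remote* is pooled with *Not Related*. The categories are not mapped to the Section 9.3.2 definition.

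Section 10.6.2 then says "All treatment-emergent adverse events (TEAEs) and SAEs will be summarized for each regimen and for all patients", broken down by system organ class, preferred term, relationship and severity.

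Every dose is given by LP (Section 8.1), and the same LP is a sampling procedure: "Patients will have CSF collected at the Screening Visit, prior to administration of each dose" (Section 6.2.18). Section 2.5 lists headache, nausea, vomiting and nerve irritation pain as known effects of LP.

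On a smaller matter, the synopsis says that safety will be assessed by the "incidence, severity and dose-relationships of AEs, ECG changes and changes in laboratory parameters by dose". Section 10.6.2 groups the tables by regimen, for example "Vital sign and ECG measures will be tabulated by regimen".

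**The concern.** The primary objective is safety and tolerability, and relationship to study drug is a planned dimension of the AE tables. If the scale has no place for a common kind of event, investigators must force it into a category whose definition it does not meet. Two of the four categories are reported together as not related. An event that satisfies the protocol's own definition of a suspected adverse reaction could therefore be counted as unrelated at one site and as drug-related at another.

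The trial makes such events easy to foresee, because drug and LP are always given together and the known LP effects are non-specific symptoms. Section 9.4.3 provides a rating of relationship to the drug but, in the text supplied, no separate rating of relationship to the procedure. An investigator has nowhere else to record that the LP may be responsible.

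**Working it through.** No sample-size or power figure bears on this point. The check is to apply the four definitions literally to each kind of event and compare the result with Section 9.3.2.

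| Event | Category met in 9.4.3.1 | Reasonable possibility (9.3.2)? |
|---|---|---|
| Clear evidence for the drug | *Related* | Yes |
| Plausible timing, no alternative | *Possible* | Yes |
| Plausible timing, alternative exists, drug likelier but unproven | None | Yes |
| Plausible timing, drug and alternative equally likely | None | Yes |
| Plausible timing, alternative more likely | *Unlikely/Remote* | A matter of judgement |
| Timing argues against the drug | *Unlikely/Remote* | Generally no |
| Readily explained, no relationship believed | *Not Related* (also *Unlikely/Remote*) | No |

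The third and fourth rows are the gap. Taking the equal case through each category:

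1. *Related* fails, because there is no clear evidence.
2. *Possible* fails, because another cause can explain the event.
3. *Unlikely/Remote* fails, because the alternative is not more likely and the timing is plausible.
4. *Not Related* fails, because the investigator does not believe that a relationship is absent.

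The case with the drug likelier fails at the same four points. The overlap in the last row does no harm, since those two categories are pooled.

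**Where this can arise.** From Appendix A, footnote 1, a fully dosed Monthly patient has 2 + 14 = 16 dosing LPs and a fully dosed Bimonthly patient has 2 + 7 = 9. Each is an occasion on which a listed LP symptom may follow a dose. If the investigator counts the LP as another cause, *Possible* is closed. If the investigator counts it as part of administration, *Possible* stays open unless some further explanation exists. The protocol does not choose between these readings.

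**Effect on the table.** The drug-related count lies between two limits: all gap events placed in *Possible*, or all placed in *Unlikely/Remote* or *Not Related*. The distance between the limits is the number of gap events, and the documents give no basis for estimating it.

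**The synopsis wording.** Regimen is the only randomised contrast (Section 4.2). The synopsis says only that the "doses used in these regimens will not exceed 120 mg/dose", and Section 8.7 says "For a given patient, no adjustment of dose is planned". Section 10.6.2 groups AEs by regimen and for all patients pooled, and ECG, laboratory results and amount of drug received by regimen. It contains no analysis by dose, and it does not defer to the SAP as Sections 10.6.3 and 10.6.4 do.

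**The case against.** The best reply on causality is that investigators do not read such scales literally. Section 9.4.3.1 judges timing against administration of the drug, and Section 2.5 says that intrathecal administration requires LP. An investigator may therefore treat the LP as part of giving the drug and rate a post-dose headache *Possible*. This stands against a stronger reading that a reader might infer, namely that every LP-type symptom after a dose necessarily has another cause and so falls in the gap. The documents do not support that. They leave the status of the LP open, which makes the rating depend on the site.

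The consequences are also contained. All TEAEs are tabulated by preferred term whatever their rating. SAEs are reported regardless of relationship (Section 9.4.1). The sponsor applies the reasonable-possibility test itself for SUSARs (Section 9.2). All of this stands. None of it repairs the investigator's rating on the CRF.

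On the synopsis, a reader might infer that no regimen table can show a dose-relationship, because LPs (16 versus 9) and post-dose Maintenance calls (14 × 2 = 28 versus 7 × 2 = 14) rise with the number of doses. For ECG and for blood and urine tests the schedule does not support this. In Maintenance, ECG is done on Days 85, 253 and 421, which are dosing days in both cohorts. Chemistry, hematology and urinalysis are taken at all 14 Maintenance clinic visits in both cohorts, before the dose when one is given. For AEs, the regimen tables validly compare the regimens as delivered, LP burden included. An additional per-dose AE table is not needed to answer this point, and it could not separate drug from LP because every dose is given by LP.

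**Conclusion.** The causality point holds. As written, Section 9.4.3.1 is stricter than Section 9.3.2 and leaves two kinds of well-timed event without a category. Drug-related counts in the relationship table of Section 10.6.2 may be too low or depend on local reading. The size cannot be quantified, and the all-event tables, SAE reporting and SUSAR judgement do not depend on it. It should be corrected, but it does not undermine the primary safety assessment.

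This rests on two assumptions. The first is that the relationship table uses the investigator's CRF rating, which Section 10.6.2 does not say in terms. The second is that no further rule exists elsewhere. A separate SAP is cited but was not among the texts available, so it may contain a mapping or grouping rule.

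The synopsis point is a minor wording mismatch and not an error of analysis. The dose level or levels used are not stated in the available text, so it cannot be settled here whether the phrase by dose was meant to refer to more than regimen.

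**What to change.** 1. Reconcile Section 9.4.3.1 with Section 9.3.2 so that *Possible* no longer requires other causes to be excluded, and so that every event meets exactly one category.
2. State in Section 10.6.2 which categories count as suspected adverse reactions in the relationship table.
3. State how effects of the LP procedure are to be rated, and carry this into the CRF guidance.
4. Flag ratings entered before the change, so that the relationship table can be read with and without them.
5. Align the synopsis wording on dose-relationships with the by-regimen tables, and keep those tables as they are.

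The cost is one definition with its CRF guidance, a sentence or two in Section 10.6.2, one synopsis sentence and a data flag. The real downside is two rating standards within one study of at most 46 patients, which the flag makes visible but does not remove.

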	Two (2) dosing regimens will be tested: the monthly regimen and the bimonthly regimen, defined above. Monthly dosing is expected to achieve steady state $RO7234292$ in the brain cortex tissue by Study Day 92 (i.e., after 4 doses). Bimonthly dosing (after 2 monthly doses to serve as a load) will be investigated to determine if sufficient pharmacological effect can be achieved with a less-frequent dosing regimen.
Adjustment of Dose and/or Treatment Schedule	Dose regimen adjustments are not planned. Any observation in a patient that causes the Investigator to propose a change in dose level or frequency must be discussed with the Sponsor Medical Monitor.
Study Visit Schedule and Procedures	After informed consent is obtained, patients will undergo necessary screening procedures within a 4-week period. Patients who meet the eligibility criteria will visit the Study Center on Study Day -1 to undergo baseline clinical, blood, and electrophysiological evaluations. On Study Day 1, patients will be admitted to the Study Center, undergo pre-dose evaluations and receive an IT bolus injection of $RO7234292$. Following this IT injection, patients will be kept at the Study Center for at least 24 hours and carefully monitored for any adverse clinical symptoms or signs. Assessments during the admission period include neurological examination, vital signs, ECGs, blood sampling, urine collection and clinical laboratory analyses. At subsequent dosing visits, patients will be monitored for at least 5 hours post-dosing prior to discharge from the Study Center. $RO7234292$ administration will take place every 28 days during the Loading
	Period and then either every 28 days or every 56 days during the Maintenance Period, according to patient randomization.
	The Study Center will monitor the patient's condition via telephone between clinic study visits. During the Post-Treatment Period, patients will visit the Study Center once (on Study Day 519) for in-clinic assessments.

	1
Study Visit Schedule and Procedures Continued	CSF samples will be taken at the Screening visit, pre-dose on each injection day and at the Post-Treatment visit. These samples will be utilized for evaluation of pharmacokinetics, Htt protein and other biomarker and laboratory analyses.
	If a patient terminates early from the Loading or Maintenance Period, he/she will be encouraged to return for the Post-Treatment Period visit (Day 519) approximately 14 weeks after last administration of RO7234292 .

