3. EXPERIMENTAL PLAN

3.1 Study Design

This study is an OLE for patients who participated in Study ISIS 443139-CS1. Study ISIS 443139-CS1 was a multiple-ascending dose (MAD) study in 46 patients with early manifest HD aged 25-65 years, inclusive. In the MAD study, patients received 4 doses of ISIS 443139 or placebo. Eligibility for Study BN40697 is based on completion of the 4-dose Treatment Period of the prior MAD study and absence of deterioration in health or intervening activities that would introduce risk to the patient sufficient to preclude participation in the OLE.

The study consists of 2 cohorts: a "Monthly Cohort" and a "Bimonthly Cohort". Both cohorts receive 2 doses of RO7234292 during the Loading Period, with doses 28 days apart. In the Maintenance Period, the Monthly Cohort continues to receive doses at 28-day intervals (14 doses over 56 weeks) and the Bimonthly Cohort receives doses at 56-day intervals (7 doses over 56 weeks). Patients will be randomized (1:1) to either the Monthly Cohort of the Bimonthly Cohort, with randomization stratified by Study Center. The cohorts will be enrolled concurrently.

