10.1.1 Safety and Tolerability Endpoints

- Columbia Suicide Severity Rating Scale (C-SSRS)
- Physical examination and standard neurological assessment (including fundi)
- Pregnancy testing
- Vital signs (heart rate [HR], BP, orthostatic changes, weight)
- ECG
- AEs and concomitant medications
- CSF safety labs (cell counts, protein, glucose)
- Plasma laboratory tests (clinical chemistry, hematology)
- Urinalysis
- Safety neuroimaging assessments

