Appendix A Schedule of Procedures Continued

Note: If not specifically labeled, "X" means anytime; ET = early termination

- * All visits windows are calculated relative Study Day 1, i.e., the date of first dose administration in this protocol. Visits with an asterisk (*) do not have a visit window and must be conducted on the exact day shown relative to the corresponding dosing day.
- ** Only patients who do not enter the open-label extension study (Study BN40955) will attend the Post-Treatment/End-of-Study visit.
- Patients are randomized to the Monthly Cohort or the Bimonthly Cohort. Patients in the Monthly Cohort receive *RO7234292* every 28 days during the Maintenance Period (14 doses in the Maintenance Period). Patients in the Bimonthly Cohort receive *RO7234292* every 56 days during the Maintenance Period (7 doses in the Maintenance Period). Study visits are shown below.

Monthly Cohort Study Visits during the Maintenance Period:

Study Weeks	Study Visit Day (Clinic Visit)	RO7234292 Dosing Visit?	Day After Dosing Visit (Phone Visit)	Seven Days After Dosing Visit (Phone Visit)
9/10	57	Y	58	64
13/14	85	Y	86	92
17/18	113	Y	114	120
21/22	141	Y	142	148
25/26	169	Y	170	176
29/30	197	Y	198	204
33/34	225	Y	226	232
37/38	253	Y	254	260
41/42	281	Y	282	288
45/46	309	Y	310	316
49/50	337	Y	338	344
53/54	365	Y	366	372
57/58	393	Y	394	400
61/62	421	Y	422	428

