- 6 If the Screening visit is conducted within 4 weeks of the patient's last visit in Study ISIS 443139-CS1 and this assessment was performed at that visit, this assessment does not need to be performed separately for Study BN40697 (i.e., the result from the patient's last visit in Study ISIS 443139-CS1 may serve as the Screening result for Study BN40697).
- 7 Ensure patient has voided bladder prior to start of *RO7234292* administration procedure. Start 24-hour urine collection immediately after *RO7234292* administration. Pool and record total urine volume.

- Stored at -80 °C for follow-up exploration of laboratory findings and/or AEs (e.g., measurement of cytokine and/or chemokine levels, measurement of additional markers of kidney function, measurement of antibodies) in this or subsequent clinical studies of *RO7234292*.
- 9 Local laboratory analysis of PT, INR, aPTT and platelets must be conducted and results reviewed prior to performing the lumbar puncture. Sample collection may occur at any time within 72 hours prior to the planned lumbar puncture.
- 10 Only at dosing visits. (See tables in Footnote 1.)
- 11 Screening CSF sample collected at least 2 weeks prior to Study Day 1. Screening sample is for Safety/Biomarkers/Archive only.

- 13 If the Screening visit is conducted within 3 months of the patient's last visit in Study ISIS 443139-CS1 and this assessment was performed at that visit, this assessment does not need to be performed separately for Study BN40697 (i.e., the result from the patient's last visit in Study ISIS 443139-CS1 may serve as the Screening result for Study BN40697).
- 14 This assessment is conducted on Study Days 85, 253 and 421 only. If necessary for ease of logistics, the assessment may be performed on a different calendar day than the dose administration (must be prior to the dose administration and within the required visit window).
- 15 If imaging is conducted after CSF collection, at least 1 day must elapse between the LP and the imaging session to avoid LP-related artifacts on the images.

Time (in reference to time of *RO7234292* administration):

- a Pre-dose; also 3 and 5 hours after administration of *RO7234292* (3- and 5-hour assessments are only performed if *RO7234292* has been administered)
- b Pre-dose at dosing visits (otherwise, at any time during the visit)
- c Approximately 24 hours after administration of RO7234292
- d Pre-dose, 0.5, 1, 2, 3, 4, 5, 6, 8 and 12 hours after administration of RO7234292

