Appendix C PK Sampling Schedule

Appendix C PK Sampling Schedule

		eriod s)		Post-Treatment Period or Early			
Study Period		Loading Period (6 weeks)		N	Termination Visit** (12 Weeks)		
Study Week	,	1	5	9-28	29	30-62	74
Study Day	1	2	29	57, 85, 113, 141, 169	197	225, 253, 281, 309, 337, 365, 393, 421	519
CSF Sampling	Pre-dose		Pre-dose	Pre-dose †	Pre-dose	Pre-dose †	Anytime
Urine Sampling	24-hour collection						

[†] Pre-dose at dosing visits only. (See tables in Appendix A, Footnote 1.)

Pre-dose at dosing visits; otherwise, sample to be collected at any time during the visit.

^{**} Only patients who do not enter the open-label label extension study (Study BN40955) will attend the Post-Treatment/End-of-Study visit.

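### CSF safety labs are sampled 15 times (Monthly) against 8 (Bimonthly) on treatment, so a by-regimen count of patients with CSF abnormalities cannot separate more looks from more doses

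*Combined protocol and SAP*

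**What the plan says.** The sampling rule is consistent across the protocol. The synopsis says "CSF samples will be taken at the Screening visit, pre-dose on each injection day and at the Post-Treatment visit". In the Appendix A Schedule of Procedures, the maintenance CSF entry carries footnote 10, "Only at dosing visits. (See tables in Footnote 1", and Appendix C marks the maintenance CSF samples "Pre-dose at dosing visits only".

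The dosing visits differ by cohort. Section 3.1 gives both cohorts two loading doses 28 days apart. The visit tables in Appendix A, footnote 1, then give Monthly patients 14 maintenance doses and Bimonthly patients 7.

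Section 10.1.1 lists "CSF safety labs (cell counts, protein, glucose") as a safety endpoint. Section 10.6.2 names the same CSF tests with chemistry, hematology and urinalysis as laboratory safety tests, to be summarized by visit and regimen. It then adds that "the number of patients who experience abnormalities in clinical laboratory evaluations will be summarized by regimen". It gives no per-sample denominator, no restriction to shared visits and no caveat about unequal sampling. Section 10.6 allows comparisons between regimens and p-values where appropriate.

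**The concern.** The number of patients with at least one abnormal result depends on how many results each patient has. Here the regimen itself fixes that number for CSF, and the Monthly cohort has almost twice as many.

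The primary objective is the safety and tolerability of the two intrathecal regimens, and CSF cells and protein are the laboratory tests closest to the injection site. A reader who sees more Monthly patients with CSF abnormalities would probably take it as a consequence of dosing frequency. The table as planned does not let the reader judge how much of a difference comes from dosing and how much from looking more often.

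**Working it through.** **Inputs**
- Dosing days: Section 3.1 and the visit tables in Appendix A, footnote 1.
- CSF baseline: the average of Screening and Day 1 (Section 10.4), so Day 1 is not a post-baseline sample.
- Enrollment: up to 46 patients randomized 1:1, about 23 per cohort (Sections 3.3 and 4.2).
- Chance p that a single CSF sample is abnormal: not given in the documents. It is assumed here, and equal in both cohorts.

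**Step 1: reproduce the plan's dose counts.** Days 57 to 421 in steps of 28 give (421 − 57)/28 + 1 = 14 Monthly maintenance doses. Days 85 to 421 in steps of 56 give (421 − 85)/56 + 1 = 7 Bimonthly doses. Both match the protocol. With Days 1 and 29 the totals are 16 and 9.

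**Step 2: count post-baseline CSF samples on treatment.** Remove Day 1 from each total.
- Monthly: Days 29, 57, 85 ... 421 = 15.
- Bimonthly: Days 29, 85, 141, 197, 253, 309, 365, 421 = 8.

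The ratio is 15/8 = 1.9. All eight Bimonthly days are also Monthly CSF days. Day 519 adds one sample for any patient who does not enter the next extension study (16 vs 9).

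**Step 3: chance of ever being abnormal at equal risk per sample.** With independent samples it is 1 − (1 − p)^n:
- p = 2%: 1 − 0.98^15 = 26% vs 1 − 0.98^8 = 15%.
- p = 5%: 1 − 0.95^15 = 54% vs 1 − 0.95^8 = 34%.
- p = 10%: 1 − 0.90^15 = 79% vs 1 − 0.90^8 = 57%.

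**Step 4: allow for within-patient correlation ρ.** Repeated samples from one patient are unlikely to be independent. Under a beta-binomial model, with a = p(1 − ρ)/ρ and b = (1 − p)(1 − ρ)/ρ, the chance is 1 − ∏(b + k)/(a + b + k) over k = 0 ... n − 1. At p = 5%:

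| ρ | Monthly (n = 15) | Bimonthly (n = 8) | Expected excess, of 23 | Monthly count higher / lower (probability) |
|---|---|---|---|---|
| 0 | 54% | 34% | 4.6 patients | 0.89 / 0.06 |
| 0.1 | 37% | 26% | 2.5 | 0.74 / 0.17 |
| 0.3 | 23% | 18% | 1.2 | 0.59 / 0.27 |
| 0.5 | 15.5% | 12.9% | 0.6 | 0.52 / 0.32 |

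The last column compares two binomial counts of 23 patients; the remainder is ties.

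**Step 5: check the other laboratory tests.** Appendix A draws chemistry, hematology and urinalysis on Day 28 and at all 14 maintenance clinic visits in both cohorts. That is 15 vs 15, so there is no gap. One count pooling all laboratory tests would dilute the CSF gap without removing it. With independent samples, CSF at 5% per sample and blood or urine at 1% per visit, it is 1 − 0.99^15 × 0.95^15 = 60% vs 1 − 0.99^15 × 0.95^8 = 43%.

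**Step 6: restrict to shared visits.** The count is then 8 vs 8 samples, and the gap due to the number of looks is zero at equal per-sample risk. Time since the previous dose still differs: from Day 85 it is 28 days (Monthly) against 56 days (Bimonthly).

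**The case against.** A reader might infer that the planned table will show a Monthly excess produced by sampling alone. The documents do not support that. CSF is drawn before each dose, so each dose except the last is followed by exactly one on-treatment sample, and samples and preceding doses rise together, 15 vs 8. If an abnormality is triggered by a dose or a puncture (Section 2.5 names infection and hemorrhage after lumbar puncture), equal risk per dose means a truly higher cumulative risk under Monthly dosing, and the count would partly show a real property of that regimen. Sampling alone explains the gap only for abnormality unrelated to dosing, and the documents do not say which kind to expect. This part of the objection stands in full.

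Four further points:
- **Whether CSF is counted.** The sentence on abnormalities does not name CSF, and the grading scale in Appendix D has no CSF parameter. Inclusion is the natural reading because the preceding paragraph lists CSF among the laboratory safety tests, but it remains an inference.
- **By-visit summaries.** Section 10.6.2 already summarizes CSF tests by visit, and Section 10.6 reports n. This gives a fair view of sample numbers at each visit, but it does not correct the patient-level count.
- **Low stakes.** There is no single primary endpoint (Section 10.1), comparisons between regimens are optional, and only CSF results are touched. This limits the weight of the point.
- **Shared visits as the main count.** Making the shared-visit count the only main result would move 7 of 15 Monthly samples to a secondary place, and it would still compare 28 with 56 days after a dose. It belongs beside the all-visit count, not in its place.

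**Conclusion.** The point holds in a limited form. The 15 vs 8 imbalance is exact. If CSF tests are in the by-regimen count, that count is expected to be higher for Monthly at any equal per-sample risk strictly between 0 and 1, unless results within a patient are perfectly correlated. It cannot tell more frequent sampling from an effect of more doses and punctures.

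The size is uncertain because p and ρ are both assumed. At p = 5% the expected excess runs from 4.6 patients of 23 (independent samples) to 0.6 (ρ = 0.5). A higher Monthly count is an expectation, not a certainty: at ρ = 0.5 the Bimonthly count would be the higher one with probability 0.32. The point does not extend to chemistry, hematology, urinalysis or by-visit summaries at shared visits. It is worth correcting because it bears on the primary safety objective and the remedy is cheap.

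**What to change.** In Section 10.6.2 or the SAP, state whether the count of patients with laboratory abnormalities includes the CSF tests. If it does, then for CSF cell counts, protein and glucose only:

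1. Keep the all-visit patient count by regimen.
2. Beside it, show for each regimen (a) abnormal samples over samples taken, and (b) the patient count restricted to the eight visits common to both cohorts (Days 29, 85, 141, 197, 253, 309, 365, 421).
3. Add a footnote: scheduled post-baseline CSF samples on treatment are 15 (Monthly) and 8 (Bimonthly); samples rise with the number of doses; from Day 85 the common-visit samples fall about 28 (Monthly) or 56 (Bimonthly) days after the previous dose; a difference in the all-visit count should therefore not be read as a regimen effect on its own.

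The cost is a short text change and two extra table lines. No new samples or visits are needed, and no Monthly finding leaves the main table.
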